#### **5.2 Study Procedures**

All study interventions will be performed in the operating room prior to the first surgical skin incision. Patients follow up visits will be conducted postoperatively in PACU.

Patients will be randomized in OnCore to one of two groups - **Group A: FIS (control), Group B: VL/FIS (intervention)**. After the patient consents and is enrolled into the study, they will be registered in OnCore and then randomized. The study team will inform the attending anesthesia provider about the subject's assigned group prior to surgery.

#### **Pre-Induction: Standard of Care (for both study arms)**

In the operating room, standard ASA monitors will be used including a pulse oximeter, an electrocardiogram and a blood pressure cuff. The attending anesthesiologist may elect to place an invasive arterial line for blood pressure measurement. General anesthesia will be induced by intravenous administration of lidocaine (1mg/kg), propofol (1-2 mg/kg), fentanyl (1-3mcg/kg), succinylcholine (1-2mg/kg), or rocuronium (0.5-1 mg/kg). Patients' lungs will be ventilated via facemask 100% oxygen until complete muscle relaxation is achieved.

#### **Post-Induction: Research Procedure (Control group-FIS)**

Following induction of general anesthesia and adequate manual ventilation, the anesthesia provider will attempt to successfully intubate the patient utilizing the flexible intubation scope. No more than 2 intubation attempts shall be made. If necessary, between intubation attempts, adequate patient ventilation will occur before the next attempt.

#### **Research Procedure (Intervention group-VL/FIS)**

Following induction of general anesthesia and adequate manual ventilation, the anesthesia provider will attempt to successfully intubate the patient utilizing both, a video laryngoscope and a flexible intubation scope. No more than 2 intubation attempts shall be made. If necessary, between intubation attempts, adequate patient ventilation will occur before the next attempt.

For both the control and intervention groups, the anesthesia provider will be given the option to secure the airway via oral pathway (passage) according to clinical judgment. If a patient's airway has not been secured within the two attempts of the respective, allocation treatment, a third attempt will be made utilizing another technique or device (as a rescue attempt) at the discretion of the anesthesia provider. At this point, no further study data will be collected, except of what device was used for the rescue attempt and any potential Adverse Events.

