| Study Procedures           | 
 
Initial study assessments will be performed in the preoperative holding area. All study interventions will be performed in the operating room prior to the first surgical skin incision. Postoperative assessments will be conducted in PACU.
 
Patients will be randomized to either study group using OnCore. Group A: FIS (control), Group B: VL/FIS (intervention). After the patient provides consent and is enrolled into the study, they will be randomized to a study group. The study team will inform the attending anesthesia
 
  |

|                            |  |
|----------------------------|--|
|                            | 
provider about the group the patient was assigned and the instruments to be utilized during intubation.
 
 
Following induction of general anesthesia and adequate manual ventilation, the anesthesia provider will attempt to successfully intubate the patient utilizing, a FIS or a combination of FIS and VL. No more than 2 intubation attempts shall be made. If necessary, in between intubation attempts, adequate patient ventilation will be performed prior to the next intubation attempt.
 
For both the control and intervention groups, the anesthesia provider will be given the option to secure the airway via oral pathway (passage) according to clinical judgment. If a patient's airway has not been secured within 2 attempts of the respective, allocation treatment, a third attempt will be made utilizing another technique or device (as a rescue attempt) at the discretion of the anesthesia provider. At this point, no further study data will be collected, except of what device was used for the rescue attempt and any potential Adverse Events.
 
   |

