### **5.3 Measurements**

Morphometric characteristics and airway assessments of all patients will be recorded in the preoperative holding area. Patients will be asked questions to assess degree of irritation. Baseline measures of blood pressure, pulse, oxygen saturation, and End-Tidal CO2 will be recorded prior to induction. Vital signs will be recorded during preoxygenation, before induction of anesthesia, after induction of anesthesia, during laryngoscopy and/or bronchoscopy, after successful intubation, and 3 times while in recovery (at PACU arrival, at 30 and 60 minutes after PACU arrival). Lastly, we will ask the same questions to the patients about degree of irritation when they're fully awake. Additionally, the anesthesiologist will provide a personal, subjective assessment following successful or failed/rescue intubation with the corresponding research procedure/technique.

**Intubation technique:** Although the time required for successful intubation is not a primary endpoint for the study, the time and number of attempts required for successful tracheal intubation will be recorded for each patient. The glottis view obtained will be recorded using the percentage of glottis opening (POGO) score. If the epiglottis is down folded and a jaw lift is required to improve view, this information will be reported. The view both before and after jaw lift will also be recorded using the POGO score. If blood or secretions are present and require suctioning, time will be stopped while suctioning occurs and this will be recorded. If rotation of the ETT to obtain intubation is required or esophageal intubation occurs, this will also be recorded. The subjective level of difficulty in the performance of intubation will also be recorded.[2]

**Intubation:** We will record how long in seconds and number of attempts required for successful endotracheal intubation in each group. An attempt is defined as an attempt at placement of an ETT through the glottic opening, pass the vocal cords, and into the trachea. Removal/reinsertion of the laryngoscope/fiberoptic scope will constitute as a new attempt. If more than 2 attempts are needed or if the anesthesia provider discontinues protocol procedures, for any reason, the case will be deemed a failure.

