#### 5.4 Outcomes definitions

**Degree of difficulty:** Difficult ETT placement is the primary outcome defined as: (i.) either first intubation time >60 seconds or (ii.) first attempt failure at intubation or (iii.) ease of intubation reported as difficult by the provider dichotomized by a scale score of 4 or 5 versus 1, 2, or 3.

**Control group-FIS placement:** A successful attempt will be defined as when the insertion tip of the FIS enters the patient's mouth (or nose), leading to placement of the ETT into the trachea and confirmation of the end-tidal CO2 capnography waveform. Any other manipulation of the airway leading to incorrect placement of the ETT will be considered a failed attempt.

**Intervention group-VL/FIS placement:** A successful attempt will be defined as when the tip of the video laryngoscope blade and insertion tip of the FIS enters the patient's mouth, leading to placement of the ETT into the trachea and confirmation of the end-tidal CO2 capnography waveform. Any other manipulation of the airway leading to incorrect placement of the ETT will be considered a failed attempt.

**Difficult intubation:** The subjective level of difficult ETT insertion termed "Ease of Intubation" measured on a Likert scale from 1 to 5, with 1 being "Extremely Easy" and 5 being "Extremely Difficult."

**Ease of ETT insertion:** The subjective level of ease of ETT passage thought glottis (from 1 = *Extremely Easy* to 5 = *Unsuccessful*) in the performance of the randomized intubation technique (FIS vs VL/FIS) will be recorded.

**Incidence of desaturation:** Incidence of oxygen saturation  $\leq 92\%$  will be recorded.

**Degree of Irritation:** The subjective level of irritation provided by the patient (0 = *None*; 1= *Mild*; 2 = *Moderate*; 3 = *Severe*) perioperatively (both pre and post operatively) will be recorded.

**Total Time:** The total time from the beginning of either FIS or FIS/VL combination insertion until successful ETT intubation in seconds, as verified by capnographic waves, chest rise and fall, and fogging of the ETT will be recorded.

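### After two failed attempts, the data-collection stop contradicts the required provider assessment and, read literally, also drops the postoperative irritation score

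*Combined protocol and SAP*

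**What the plan says.** Section 5.2, in the paragraph that applies to both groups, provides for a rescue attempt when the airway is not secured within two allocated attempts. It continues: "At this point, no further study data will be collected, except of what device was used for the rescue attempt and any potential Adverse Events". The Summary Table repeats this sentence under Study Procedures.

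Elsewhere the plan schedules measurements that fall after that moment:

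- Section 5.3 states that "the anesthesiologist will provide a personal, subjective assessment following successful or failed/rescue intubation with the corresponding research procedure/technique".
- Section 5.3 also sets three vital-sign readings in recovery (PACU arrival, 30 and 60 minutes) and adds: "Lastly, we will ask the same questions to the patients about degree of irritation when they're fully awake".
- Section 5.4 defines Ease of ETT insertion on a scale whose top level, 5, is Unsuccessful, and says that this rating "in the performance of the randomized intubation technique (FIS vs VL/FIS) will be recorded". It defines the 0-to-3 degree of irritation, which "perioperatively (both pre and post operatively) will be recorded".
- Section 5.2 says "Patients follow up visits will be conducted postoperatively in PACU", and the Summary Table says "Postoperative assessments will be conducted in PACU". Neither sentence excludes failed cases.

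No section says which rule prevails.

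**The concern.** Study staff cannot follow both instructions for the provider's assessment. For the PACU readings and irritation questions they must guess whether the stop rule overrides the general schedule, and different staff may guess differently.

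Failing twice happens after randomisation and may itself depend on the assigned technique. If those patients are not asked about irritation, the comparison is no longer between the groups as randomised. Section 1.2 lists hoarseness, soreness, dysphonia and dysphagia among the secondary objectives, and section 2.6 names less postoperative sore throat as an expected benefit. The irritation score plausibly serves that objective, but this is an inference: neither text refers to the other, and sections 10.2 and 10.3 state no analysis of irritation. Questions not asked in PACU cannot be recovered later.

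**Working it through.** **1. The texts side by side**

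| Item after two failed attempts | Stop rule, read literally | Other sections | Relation |
|---|---|---|---|
| Provider's assessment | Not among the exceptions, so not collected | 5.3 requires it after a failed or rescue intubation; 5.4 provides a level for failure | Direct contradiction |
| Three PACU readings | Not collected | 5.3 schedules them; failed cases neither named nor excluded | No explicit contradiction; dropped if the stop rule is applied |
| Awake irritation questions | Not collected | As for the PACU readings | As for the PACU readings |
| Adverse events | Collected | 7.3 records them with severity; 7.2 lists dental damage | None |

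**2. What is not touched**

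A patient who fails twice has failed the first attempt and so already meets criterion (ii) of the primary outcome. The failure itself is recorded under section 5.3. The sample size rests on the primary outcome alone. The plan has no figure on the present point. Its 60 per arm (section 10.1), used below as the denominator, reproduces: a pooled normal approximation gives 62 per arm, and exact power of the uncorrected chi-square test at 60 per arm is 80.2%.

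**3. Irritation: how far the collected comparison could be from the randomised one**

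The documents give neither a two-attempt failure rate nor a symptom rate, so all inputs except n = 60 are assumptions. Irritation is reduced to symptoms yes/no for illustration only; the plan sets no such cut-point. Differences are FIS minus VL/FIS.

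With k patients not collected and rate s in the rest, the rate among all randomised lies between (n - k)s/n and [(n - k)s + k]/n. Take s = 30% in both arms, so that the collected difference is 0.

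- FIS, k = 6: 54 × 0.30 = 16.2, giving 16.2/60 = 27.0% to 22.2/60 = 37.0%.
- VL/FIS, k = 2: 58 × 0.30 = 17.4, giving 17.4/60 = 29.0% to 19.4/60 = 32.3%.
- Difference: 27.0 - 32.3 = -5.3 to 37.0 - 29.0 = +8.0 points. The width is (6 + 2)/60 = 13.3 points.

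Other assumed losses:

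- 3 v 1: FIS 28.5% to 33.5%, VL/FIS 29.5% to 31.2%; difference -2.7 to +4.0.
- 12 v 3: FIS 24.0% to 44.0%, VL/FIS 28.5% to 33.5%; difference -9.5 to +15.5.
- If VL/FIS lost 6 and FIS 2, the signs reverse: -8.0 to +5.3.

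The direction depends on symptoms after failure. With 6 v 2 lost, the rate among all randomised is [(n - k) × 0.30 + k × s_fail]/n:

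| s_fail (assumed) | FIS | VL/FIS | Difference |
|---|---|---|---|
| 60% | (16.2 + 3.6)/60 = 33.0% | (17.4 + 1.2)/60 = 31.0% | +2.0 |
| 30% | 30.0% | 30.0% | 0 |
| 15% | (16.2 + 0.9)/60 = 28.5% | (17.4 + 0.3)/60 = 29.5% | -1.0 |

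Exact power of the uncorrected two-sided chi-square test for 33.0% v 31.0% with 60 per arm is 5.8%. The issue is the estimate, rarely the test result.

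**4. Ease of ETT insertion**

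Leaving out a fraction f of patients scored 5 lowers an arm's mean by f(5 - m), where m is the mean in the rest. With m = 2.5 (assumed): 6/60 × 2.5 = 0.25 against 2/60 × 2.5 = 0.08, a gap of 0.17 points. This arises only if the analyst discards a score that the recorded failure largely supplies.

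**The case against.** The stop sentence directly follows the rescue sentence and may have been meant only for procedural data on the rescue attempt. Section 5.3 names failed cases for the provider's assessment alone. For the PACU readings and irritation questions, a specific stop for a defined subgroup can be read as an ordinary exception to a general schedule. Reported injuries and symptoms are kept as adverse events, including those elicited from the patient. Irritation after rescue also reflects the rescue device, which could be a reason to stop. No irritation analysis is stated, and no outcome is said to use the PACU readings; the desaturation definition in section 5.4 gives no time window.

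Most of this stands. It confines the direct contradiction to one item, and it shows that tooth damage and other reported injuries are not lost. Two things remain:

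- The narrow reading is not what the sentence says. Had only rescue-procedure data been meant, adverse events would not have needed listing as an exception.
- Adverse-event reports do not replace the same pre- and postoperative questions asked of every other patient.

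A reader might infer that sections 5.2 and 5.3 contradict each other on all three items. The documents do not support that, because section 5.3 is silent on failed cases for two of them.

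**Conclusion.** The concern holds in limited form. There is a direct contradiction on the provider's assessment after two failed attempts. For the PACU readings and the irritation questions there is an ambiguity that, resolved literally, leaves the postoperative irritation score missing in a subgroup formed after randomisation. The link to the secondary symptom objective is an inference. The size and direction of any bias are unknown. The figures above illustrate what assumed failure and symptom rates would imply and are not estimates for this trial.

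Two stronger conclusions might be drawn and are not supported. One is that the primary comparison is damaged: criterion (ii) already captures these patients, so the primary outcome, sample size, power and failure rate are unaffected. The other is that the ease scale is materially biased: a score of 5 can largely be read from the recorded failure, and the scale is exploratory. The point is minor and limited to secondary and exploratory data.

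**What to change.** Reconcile the Summary Table and section 5.2 with section 5.3:

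- Limit the stop to procedural data on the rescue attempt, in both places.
- State that the provider's rating of the allocated technique, the scheduled PACU readings and the awake irritation questions are still collected after two failed attempts.
- Add one sentence to section 10: irritation and Ease of ETT insertion are compared by assigned arm with failed cases included, the latter scored 5.

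The cost is wording in three places and the already planned questions and readings in a few more patients (6 + 2 = 8 in the main illustration). Irritation in those patients will partly reflect the rescue device, which should be noted when reporting. No new procedure is added and rescue management does not change.

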### **5.3 Measurements**

Morphometric characteristics and airway assessments of all patients will be recorded in the preoperative holding area. Patients will be asked questions to assess degree of irritation. Baseline measures of blood pressure, pulse, oxygen saturation, and End-Tidal CO2 will be recorded prior to induction. Vital signs will be recorded during preoxygenation, before induction of anesthesia, after induction of anesthesia, during laryngoscopy and/or bronchoscopy, after successful intubation, and 3 times while in recovery (at PACU arrival, at 30 and 60 minutes after PACU arrival). Lastly, we will ask the same questions to the patients about degree of irritation when they're fully awake. Additionally, the anesthesiologist will provide a personal, subjective assessment following successful or failed/rescue intubation with the corresponding research procedure/technique.

**Intubation technique:** Although the time required for successful intubation is not a primary endpoint for the study, the time and number of attempts required for successful tracheal intubation will be recorded for each patient. The glottis view obtained will be recorded using the percentage of glottis opening (POGO) score. If the epiglottis is down folded and a jaw lift is required to improve view, this information will be reported. The view both before and after jaw lift will also be recorded using the POGO score. If blood or secretions are present and require suctioning, time will be stopped while suctioning occurs and this will be recorded. If rotation of the ETT to obtain intubation is required or esophageal intubation occurs, this will also be recorded. The subjective level of difficulty in the performance of intubation will also be recorded.[2]

**Intubation:** We will record how long in seconds and number of attempts required for successful endotracheal intubation in each group. An attempt is defined as an attempt at placement of an ETT through the glottic opening, pass the vocal cords, and into the trachea. Removal/reinsertion of the laryngoscope/fiberoptic scope will constitute as a new attempt. If more than 2 attempts are needed or if the anesthesia provider discontinues protocol procedures, for any reason, the case will be deemed a failure.

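### Does a scope withdrawn for suction leave the first attempt, and so the primary outcome, undefined?

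*Combined protocol and SAP*

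**What the plan says.** The primary outcome, difficult tube placement, is met by any one of three components (Section 5.4, Degree of difficulty). The first two read "i.) either first intubation time >60 seconds or (ii.) first attempt failure at intubation"; the third is a provider ease score of 4 or 5.

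Section 5.3 supplies the rules for time and attempts:

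- Clock: "If blood or secretions are present and require suctioning, time will be stopped while suctioning occurs and this will be recorded".
- Meaning of an attempt: "An attempt is defined as an attempt at placement of an ETT through the glottic opening, pass the vocal cords, and into the trachea".
- Counting rule, in the next sentence: "Removal/reinsertion of the laryngoscope/fiberoptic scope will constitute as a new attempt".
- Case failure: "If more than 2 attempts are needed", or if the provider discontinues the protocol procedures, the case is a failure.

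Section 5.4 defines a successful attempt in each arm as one that leads to the tube in the trachea with a capnography waveform. It then adds: "Any other manipulation of the airway leading to incorrect placement of the ETT will be considered a failed attempt". The same attempt count feeds the secondary outcomes in Section 1.2 (number of attempts, rate of failure) and one of the three Total Score items in Section 5.4.

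**The concern.** Suction appears in Section 5.3 only as an interruption of the clock, which suggests that the intubation under way continues afterwards. The counting rule has no exception for suction. The definition of an attempt refers to placing a tube, so a scope withdrawn before the tube moves might be argued not to have used up an attempt. The failed-attempt sentence in Section 5.4 mentions incorrect tube placement, and here no tube was placed. Three codings of one patient then seem possible, and they do not all give the same primary outcome.

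If staff followed different sentences, first-attempt failure would mean different things from patient to patient. The number of attempts, the failure rate and the Total Score could shift as well. Two smaller loose ends concern the clock. The VL/FIS success definition starts "when the tip of the video laryngoscope blade and insertion tip of the FIS enters" the mouth, which names two instruments. Total Time ends "as verified by capnographic waves, chest rise and fall, and fogging of the ETT", whereas the success definition names capnography alone.

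**Working it through.** **Worked case (illustrative times).** Scope in for 20 s, withdrawn, suction for 20 s, reinserted, tube placed 35 s later, ease score 3. Net time is 20 + 35 = 55 s; elapsed time is 20 + 20 + 35 = 75 s. On net time, neither the time component nor the ease component is met.

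| Reading | Attempts | First-attempt failure? | Primary outcome |
|---|---|---|---|
| A. Pause only, same attempt | 1 | No | Not difficult |
| B. New attempt, first one failed | 2 | Yes | Difficult |
| C. New attempt, first one not called failed | 2 | No | Not difficult |

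**Reading A.** The suction sentence speaks only of time. Nothing in it preserves the attempt count. The counting rule is explicit and unqualified, and it directly follows the general description of an attempt, so it is the operational version of that description. A requires that rule to be ignored. Applying both sentences as written gives 55 s net and two attempts. The attempt count and the Total Score item are then settled. With two such withdrawals the count is three, and the case-failure rule applies.

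**B against C.** The failed-attempt sentence says that incorrect tube placement is a failure. It does not say that nothing else is. Under C, a patient needs a second attempt although the first neither succeeded nor failed. B is the ordinary meaning of first-attempt failure.

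**Planned design (Section 10.1).** With 60 per arm, rates of 0.30 and 0.10, and two-sided alpha 0.05:

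- Power = Φ[(0.20·√60 − 1.96·√(2·0.20·0.80)) / √(0.30·0.70 + 0.10·0.90)] = Φ[(1.549 − 1.109)/0.548] = Φ(0.804) = 0.789.
- Exact enumeration of the uncorrected chi-square test gives 0.802. The stated 80% is reproduced.

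**How many reclassified patients would matter.** Take the planned result, 18/60 against 6/60, and use χ² = (p₁ − p₂)² / [p̄(1 − p̄)·2/60], with critical value 3.841.

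| Counts (FIS v VL/FIS) | Change from plan | χ² | p |
|---|---|---|---|
| 18 v 6 | none | 0.0400/0.005333 = 7.50 | 0.0062 |
| 18 v 9 | 3 added, VL/FIS only | 0.0225/0.005813 = 3.87 | 0.0491 |
| 18 v 10 | 4 added, VL/FIS only | 0.01778/0.005963 = 2.98 | 0.0842 |
| 15 v 6 | 3 removed, FIS only | 0.0225/0.004813 = 4.68 | 0.0306 |
| 14 v 6 | 4 removed, FIS only | 0.01778/0.004630 = 3.840 | 0.0500 |
| 36 v 24 | 18 added to each arm (worst equal case) | 0.0400/0.008333 = 4.80 | 0.0285 |

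Equal numbers added to both arms never reverse the decision. Four patients reclassified in one arm and none in the other would do so, and the 14 v 6 case misses the critical value by only 0.001.

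**Clock markers.** Total Time runs from the beginning of insertion of the FIS or of the combination, which most naturally means the first instrument in. The end markers all verify the same event, a tube in the trachea. The choice could matter only for times close to 60 s, and the documents give no figure for that. The remark in Section 5.3 that time to successful intubation is not a primary endpoint fits Section 5.4, where only the 60-second cut on the first intubation enters the composite.

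**The case for a change.** The best case for a change is that B and C both obey the counting rule and still classify the same patient oppositely. Applying both sentences of Section 5.3 therefore does not fully settle the primary outcome. One sentence would close the gap. Section 5.3 asks for suction, time and number of attempts to be recorded, but not for whether the scope came out or whether the tube had been advanced, so later recoding could be hard. The provider also knows the allocation.

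An illustration can be added. Assume that 30% and 10% are rates under the pause reading, and that a share s of otherwise not-difficult patients has a withdrawal that is then counted as failure. The rates become 0.30 + 0.70s and 0.10 + 0.90s:

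- s = 5% in both arms: 33.5% v 14.5%, power 0.69.
- s = 10% in both arms: 37% v 19%, power 0.60.
- s = 20% in both arms: 44% v 28%, power 0.45.
- s = 10% FIS and 5% VL/FIS: 37% v 14.5%, power 0.81.
- s = 5% FIS and 10% VL/FIS: 33.5% v 19%, power 0.44.

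It stands that Section 5.4 does not expressly classify a first attempt withdrawn before tube passage, for suction or any other reason. The rest is weaker. Every value of s is assumed, and Section 10.1 does not tie its 30% to the pause reading. The figures compare two definitions of the outcome; they do not measure harm from unclear wording. If one rule is applied in both arms, a difference in withdrawals between arms is part of what the trial compares. Bias would need the rule to be applied differently by arm, and nothing in the documents shows that. No passage says that suction requires withdrawing the scope, and suction with the scope in place is a clock pause only. The recorded number of attempts already identifies anyone who needed a second one.

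**Conclusion.** The concern does not hold as a conflict. The clock rule and the counting rule apply together, and reading A has to disregard an explicit sentence. What is left is a narrow gap in wording: a first attempt that ends without tube passage is not named as failed. Coders would ordinarily fill it by treating any first attempt that did not succeed as a failure. Writing that down would be harmless, but it records what would be done anyway.

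The gap can alter the primary outcome only for patients with net time of 60 s or less and ease 1 to 3, at 1.7 percentage points of an arm each. From the planned result, four such patients in one arm and none in the other would be needed to reverse the test. The conclusion assumes that the counting rule is applied as written in both arms. The frequency of withdrawal is unknown, so no effect on bias, power or sample size is established.
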